16.1. CRFs/EDC

[figure not shown]
This study will utilize an electronic data capture (EDC) system to manage data collection during this trial. The system is fully Code of Federal Regulations 21 part 11 compliant. This EDC will reside behind the Zone 100 UTHealth firewall with Shibboleth-based user-access and identification. Patients will be assigned a unique ID number. A master key file will be stored on the shared password protected drive at UTHealth. Only Co-investigators at UTHealth and their staff (to be added through amendment at a later date when hired) will have access to this master key file.

The EDC in this study will utilize the REDcap system maintained on secure UTHealth servers. This database possesses a graphical user interface to facilitate data entry, capability of tracking data management and user activity, a data validation element to check user data (e.g. impermissible/outof-range or missing values), and a reporting function to assist with the review and analysis of data. The data base will utilize a relational structure to avoid so-called "orphan records" with staff password protected and access to and modification of data tables restricted based on their operational roles. Clinical Research Forms (CRF's) available through this system are required and will be completed for each randomized subject. Any data from the electronic system are the sole property of the sponsor and will not be made available in any form to third parties, except for authorized representatives of the sponsor or appropriate regulatory authorities, without written permission from the sponsor. The investigator has ultimate responsibility for the accuracy, authenticity, and timely collection and reporting of all clinical, safety, and laboratory data entered in the EDC or any other data collection forms. The CRFs will be signed electronically by the investigator to attest that the data contained on the CRFs are true.

In most cases, the source documents are contained in the subject's chart at the hospital, dialysis or research clinic, or the physician's office. In these cases, data collected on the CRFs will match the data in those charts.

16.2. Record Retention

To enable evaluations and/or audits from regulatory authorities or the sponsor, the investigator agrees to keep records, including the identity of all participating subjects (sufficient information to link records, e.g., CRFs and hospital records), all original signed informed consent forms, copies of all CRFs, SAE forms, source documents, detailed records of drug disposition, and adequate documentation of relevant correspondence (e.g., letters, meeting minutes, and telephone calls reports). The records will be retained by the investigator according to the International Conference

of/Council for Harmonisation (ICH) of Technical Requires for Pharmaceuticals for Human Use local regulations, or as specified in the Clinical Study Agreement, whichever is longer.

If the investigator becomes unable for any reason to continue to retain study records for the required period (e.g., retirement and relocation), the sponsor will be prospectively notified. The study records will be transferred to a designee acceptable to the sponsor, such as another investigator, another institution, or to the sponsor. The investigator will obtain sponsor's written permission before disposing of any records, even if retention requirements have been met.

17. Quality control and assurance

17.1. Manufacture and Storage

Drug to be tested: Vadadustat is manufactured by Akebia and contains microcrystalline cellulose (MCC), sodium starch glycolate, hydroxypropyl methylcellulose (HPMC), colloidal silicon dioxide, and magnesium stearate, and a nonfunctional film coat in addition to vadadustat. Placebo: Placebo is manufactured by Akebia and contains MCC, colloidal silicon dioxide, magnesium stearate, and a nonfunctional film coat. Vadadustat and placebo are stored at room temperature.

17.2. Active Dose

Subjects will receive 900 mg as 6 x 150 mg tablets once daily.

17.3. Dispense and Handling of Study Drug

The research pharmacist or designee will dispense 6 tablets of vadadustat or placebo daily for each study patient. Administration to the study patients will follow the local institution's procedures.

18. Protocol Amendment

18.1 Long-Term Follow-up

[figure not shown]
The purpose of this amendment is to characterize the long-term effects on COVID-19 survivors who were hospitalized with SARS-CoV-2 and treated with either a HIF activator vadadustat or placebo. Specifically, we will 1) characterize the occurrence of long-term COVID-19 sequelae in a well-described patient cohort and 2) address the hypothesis that vadadustat would attenuate or prevent the long-term disease sequelae of SARS-CoV-2.

18.2 Study Objectives.

Primary: Evaluation of pulmonary capacity as a function of treatment, time and the interaction of treatment and time.

Secondary: Evaluate cardiac, hepatic and renal outcomes, quality of life, and long-term neurocognitive impairment of COVID-19 patients treated with either vadadustat or placebo

18.3 **Study Diagram.**

18.4 **Study Population.**

Eligibility Criteria

18.4.1 Inclusion Criteria

- Male or Female age ≥ 18 .
- Previously enrolled in the vadadustat study and agreed for an extended follow-up. •
- Patients who Speak/Write in English or Spanish •

18.4.2 Exclusion Criteria

- Patients who were enrolled in the vadadustat study but withdrew before taking the 1st dose of the study drug.
- Patients who were enrolled in the vadadustat study but did not consent for an extended follow-up.
- Patients who do not speak English or Spanish. •

18.5 **Data Collection.**

The following will be collected on the 6th, 12th and 24th month follow-up.

Informed consent for the extended follow-up shall be referenced to the IRB approved ICF of vadadustat study starting February 5, 2021 wherein patients have agreed to participate in this long-term study.

For those patients consented prior to February 5, 2021, please refer to Section 18.9 of the study protocol for the reconsenting process.

- Body Mass Index, height, weight •
- Medication History
- Tobacco use •
- Past Medical History
- Laboratory Tests: ALT, AST, Total Bilirubin, Creatinine, and Hemoglobin. •
- Cardiac, Renal and Lung Biomarkers (Blood and urine) •

Pulmonary Function test

- Transthoracic echocardiography (TTE)
- Lung ultrasound
- PROMIS Scale v1.2 Global Health Survey
- MoCA Test (Montreal Cognitive Assessment)

18.6 Study Procedures.

Each study participant will undergo the following procedures on 6th, 12 and 24th month follow- up. There is a one (1) month window to complete each follow up appointment once a patient reaches their long term follow up due date. This one-month window provides flexibility to schedule and accommodate both the patient and the clinical teams' availability. If a patient cannot be scheduled within one month of their follow up date, this will be deemed a loss to follow up and documented in RedCAP accordingly.

18.6. 1 Sample collection processing

Blood and urine samples will be collected at our Clinical Research Unit (CRU) and processed using standard protocols. Blood specimens will be collected from the patient (biomarkers and laboratory specific tests) and urine over the course of the visit. Universal precautions and institutional biosafety procedures will be followed.

18.6.2 Transthoracic Echocardiography (TTE)

This test is the primary noninvasive imaging modality for quantitative and qualitative evaluation of cardiac anatomy and function using an ultrasound. This test will be performed by physicians, fellowship-trained in ultrasonography.

The study currently evaluates pulmonary function and cardiac function as part of the long term follow up protocol. There is currently no lung imagining as part of the follow up process. Previous literature has shown ultrasound is as accurate as computed tomography for interstitial lung disease, without the cost or ionizing radiation. We are adding lung ultrasound as a seamless addition to the echo portion of the long term follow up study. We anticipate this exam will add approximately five minutes to the ultrasound portion of the protocol. There are no known harms associated with lung ultrasound.

C60 probe using abdominal preset. Axial images obtained via cranial caudal sweep of the right and left hemi-thorax in the mid-clavicular, mid-axillary, and peri-scapular. De-identified video clips of each location will be saved. We will make notation of any unusual signature with particular attention to previously described findings in COVID lung disease including B lines and sub-pleural consolidations.

Data Collection Sheet:

	R Midclav	L Midclav	R Midax	L Midax	R Periscap	L Periscap
3+ B lines						
Confluent B						
Lines						
Sub-pleural						
Conolidation						
Pleural						
Effusion						

Check mark indicates present of the finding

Other findings:

18.6.3 Pulmonary Function Tests

Participants will be subjected to a pulmonary testing using spirometry. Briefly, spirometry is used to measure forced expiratory flow rates and volumes. It is the most commonly used pulmonary function test and is useful in the evaluation of patients with respiratory symptoms (e.g., dyspnea, cough, wheeze) or risk factors for respiratory diseases. Specifically, we will be measuring FVC, FEV, FEV/FVC ratio.

18.6.4 Study Questionnaires

The PROMIS Global Health assess an individual's physical, mental and social health. The measures are generic, rather than disease-specific, and often use an 'In General' item context as it is intended to globally reflect individuals' assessment of their health. The adult PROMIS Global Health measure produces two scores: physical health and mental health. The Montreal Cognitive Assessment (MoCA) is a tool to assess short memory, visuospatial abilities, executive functions, attention, concentration and working memory, language and orientation to time and place.

18.6.5 Visit Compensation

Each time a patient completes follow up, she/he will receive a \$100 gift card, (up to a maximum of \$300 for completion of 3 follow-up in 24 months). Patients will be provided with a \$100 SPA Card at the end of each visit. Additionally, the study team will arrange round trip transportation of the patient from and to their home or destination. Should they choose to drive, the research team will provide patients with parking validation.

18.6.6 Study Dissemination

Study clinicians will review any results found outside of expected ranges for the Transthoracic Echocardiography, pulmonary function test, lung ultrasound, labs and/or MoCA. Participants will be notified via mail to follow up with their PCP.

18.7 Withdrawal from Follow-up Visits

A patient can withdraw from participating in the long-term follow-up at any point for any reason. If possible, reasons for discontinuation or refusal will be documented.

18.8 Statistics

18.8.1 Specific Statistical Hypothesis of Primary Outcome

The primary outcome analysis will model pulmonary capacity as a function of time, treatment and the interaction of time and treatment after controlling for stratification variables (i.e. site and MSOFA < 4 or \ge 4).

18.8.2 Sample Size and Power Calculation

For the purpose of sample size justification, we assume a small between-groups effect (Cohen's d = 0.2) unfolding in linear fashion over time (6, 12, and 24 months). Estimation will focus on the interaction of treatment and time to ascertain the degree to which the two group's trajectories of change differ. We further assume that pulmonary function will exhibit with subject autocorrelation of r = 0.3 for every six-month time lag with this correlation diminishing by 50% for every additional six-month time lag. We anticipate enrolling N = 200 participants, and assume attrition will be approximately 10% resulting in a final sample of n = 180. Stipulating a posterior probability of 0.80 for the existence of an interaction effect (i.e. there is an 80% chance that there are differential trajectories of change for the treatments, K = 1000 Monte Carlo simulations identify an interaction term 92% of the time.

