13.2. Bayesian Modeling Strategy

Initial analyses examining group differences for baseline variables will use cross-tabulation, ANOVA's, and examination of correlations between baseline variables and specified outcomes. For the purposes of evaluating the comparability of groups, a posterior probability of > 95% will constitute evidence for statistically reliable differences. Baseline or demographic variables on which group differences are detected, and which are correlated with outcomes, meet the definition of confounders (Assmann et al 2005, Pocock et al 2002) and will result in two sets of analyses: one in which the relevant variable is included as a covariate and one in which it is not. This will permit determination of the degree to which any group differences might confound conclusions regarding treatment.

Broadly, the data analytic strategy will use generalized linear and multilevel models (R v. 3.6, and Stan 2.17) for both discrete and continuous outcomes (SAS Institute 2002-2012, R Core Team 2017, Carpenter et al 2017). Multilevel generalized linear modeling to account for clustering of patients within site and repeated observations within patients will evaluate continuous, dichotomous, and count data. All analyses will apply intention-to-treat principles with missingness addressed via joint modeling of observed outcomes and the missing data, an approach robust to ignorable missingness (i.e., MCAR and MAR) (Best & Thomas 2000). Sensitivity analyses will evaluate robustness of analytic conclusions to missing data. Non-ignorable missing data patterns will be addressed through pattern-mixture modeling methods (Fitzmaurice & Laird 2000). Evaluation of posterior distributions will permit statements regarding the probability that effects of varying magnitudes exist, given the data. Specification of diffuse, neutral priors will reflect the initial uncertainty regarding effect sizes. For all generalized linear models, priors for regression coefficients will be specified as ~Normal ($\mu=0, \sigma 2=1 \times 10$), level one and two error variances will be specified as ~Half-Normal ($\mu=0, \sigma 2=1 \times 10^3$). The choice of prior distribution for level two variances will follow Gelman's recommendations (Gelman 2006). Priors for the comparison of proportions will be specified as ~Beta (α =1.0, β =1.0).

14. Ethics

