18.8.3 Linear Multilevel Models

Analyses will focus on longitudinal trajectories of change for outcomes specified in objectives 1-3. Generalized linear multilevel models will evaluate change as a function of time, treatment, and the interaction of treatment and time after controlling for stratification variables (i.e. site and baseline severity as measured by the MSOFA < 4 or \geq 4). Analyses will utilize Bayesian inference. Prior distributions will be neutral (centered on the null hypothesis) and weakly informative as described by Gabry and Goodrich (2020). This will have the benefit of regularizing any parameter estimates and render more conservative estimates of effect size. Regarding priors essentially as a set of assumptions, we will evaluate the robustness of our analytic conclusions to alternative prior specifications with varying degrees of regularization/skepticism (Gelman, 2007; Spielgelhalter, 2004).

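### The long-term focus, the 0.80 posterior and the 92% figure all rest on a treatment-by-time interaction with no stated sign, which answers only part of the long-term hypothesis

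*Combined protocol and SAP*

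**What the plan says.** Section 18.1 sets a directional hypothesis for the follow-up: to "address the hypothesis that vadadustat would attenuate or prevent the long-term disease sequelae of SARS-CoV-2". The primary objective in section 18.2 names three terms: "Evaluation of pulmonary capacity as a function of treatment, time and the interaction of treatment and time". Section 18.8.1 carries all three into the model: "The primary outcome analysis will model pulmonary capacity as a function of time, treatment and the interaction of time and treatment".

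Section 18.8.2 narrows this to one term: "Estimation will focus on the interaction of treatment and time to ascertain the degree to which" the two arms' courses differ. The 0.80 posterior is stipulated for the existence of an interaction and glossed as "there is an 80% chance that there are differential trajectories of change for the treatments". The operating characteristic is for the same term: "K = 1000 Monte Carlo simulations identify an interaction term 92% of the time". Section 18.8.3 keeps the emphasis: "Analyses will focus on longitudinal trajectories of change for outcomes specified in objectives 1-3".

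The plan's other posterior criteria are 0.85 for the day-14 outcome (section 12) and 95% for baseline comparability (section 13.2). Neither applies to the long-term treatment term. Section 13.2 does provide generally that "Evaluation of posterior distributions will permit statements regarding the probability that effects of varying magnitudes exist, given the data".

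Drug is given for at most 14 days (section 7.4.2). Pulmonary function testing is listed at months 6, 12 and 24 (sections 8.4.1 and 18.5). Section 8.4 lists none earlier. Appendix 1 was not in the text available to me.

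**The concern.** An effect on sequelae can take three simple forms over these visits: a gap that grows after month 6, a gap already present at month 6 and held, or a gap present at month 6 that closes as placebo patients catch up. Treatment ends by day 14 and the first listed lung function value is months later, so the second and third forms are quite possible. The interaction responds as intended only to the first. It is blind to the second and changes sign for the third.

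Because the 0.80 statement asks only whether trajectories differ, a growing benefit and a fading one would meet it equally. A report that follows the stated focus could therefore show nothing for a maintained benefit, or a difference in slopes that is easily misread for a fading one. The quantity that would settle the reading, the difference in level, has no planned contrast.

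**Working it through.** **Inputs.** N = 200 less 10% attrition gives 180 (section 18.8.2). I take 90 per arm, assuming the 1:1 allocation of section 4 carries over. Correlations (section 18.8.2): 0.30 at a 6-month lag, halving with each further 6 months. That gives 0.30 (months 6 and 12), 0.15 (12 and 24) and 0.075 (6 and 24). Further assumptions: outcome SD 1, flat prior, no covariate adjustment.

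**Method.** The three visit differences between arms have covariance V = 2R/90. A line in months is fitted by generalised least squares: b = (X'V⁻¹X)⁻¹X'V⁻¹d. The standard error of the fitted change in the gap from month 6 to month 24 is 0.2015 SD. With z = Φ⁻¹(0.80) = 0.842, P(flagged favourable) = Φ(δ/SE − 0.842) and P(flagged unfavourable) = Φ(−δ/SE − 0.842).

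**The plan's 92%.** It does not reproduce from the stated inputs, because the text does not say over what interval d = 0.2 accrues. In one direction:

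| d = 0.2 read as | Detection |
|---|---|
| reached at month 24, from 0 at month 0 | 46% |
| reached at month 24, from 0 at month 6 | 56% |
| per 12 months | 74% |
| per visit | 86% |
| per 6 months | 98% |

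A rate of 92% needs a change from month 6 to 24 of (0.842 + 1.405) × 0.2015 = 0.45 SD. Nothing below depends on the 92%.

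**Maintained benefit, 0.2 SD at every visit.** The change in the gap is 0, so P = Φ(−0.842) = 20% in each direction, or 40% if the sign is ignored. No effect gives the same figures, and so does a maintained 0.5 SD.

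**Fading benefit, 0.2 SD at month 6 falling linearly to 0 at month 24.** δ/SE = −0.2/0.2015 = −0.993. Flagged unfavourable: Φ(0.993 − 0.842) = 56%. Flagged favourable: Φ(−0.993 − 0.842) = 3%.

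**Averaged level difference, maintained 0.2 SD.** SE² = (2/90) × [3 + 2(0.30 + 0.15 + 0.075)]/9 = 0.0222 × 0.45 = 0.0100, so SE = 0.100. The chance that P(benefit) exceeds 0.80 is Φ(0.2/0.100 − 0.842) = 88%. For a constant correlation r (assumed range), SE² = (2/90)(1 + 2r)/3:

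| r | SE | Chance P(benefit) > 0.80 |
|---|---|---|
| 0.3 | 0.109 | 84% |
| 0.5 | 0.122 | 79% |
| 0.8 | 0.139 | 73% |

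A neutral Normal prior of SD 0.5 or 0.2 on this difference (assumed) moves 88% to 87% or 86%.

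**If thresholds were attached to both contrasts.** Their estimates are nearly uncorrelated, so with no effect the chance of at least one favourable flag is about 1 − 0.8² = 36% at 0.80 each, or 1 − 0.9² = 19% at 0.90 each. For a gap growing from 0 to 0.2 SD, the interaction is detected in Φ(0.993 − 0.842) = 56% at 0.80, but in Φ(0.993 − 1.282) = 39% at 0.90.

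**Selection.** With no drug effect and a 0.10 SD shift between the followed arms (assumed), the averaged contrast is favourable in Φ(0.10/0.100 − 0.842) = 56% of trials. The interaction stays at 20%.

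**The case against.** The sponsor assumed an effect that unfolds linearly over the visits, and sizing the interaction follows from that. For a gap growing from 0 to 0.2 SD the interaction is the better contrast: 56% against 52% for the average at the plan's correlations, and 91% against 42% at constant correlation 0.8. Change is also less exposed to selection: about 200 of 650 patients are expected, all consenting survivors, with no earlier spirometry listed. Both arguments stand, and they are why the interaction should remain the sized term.

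Four stronger readings are tempting, and the documents do not support them.

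- *The treatment effect is not analysed.* It is in the objective and the model, and section 13.2 allows probability statements about effects. A maintained benefit would be estimated.
- *0.80 is the long-term success rule.* It is introduced to justify sample size, although it is the only long-term threshold given. Sections 18.8.1 and 18.8.3 state no success rule for any term.
- *The unstated time origin is itself a defect.* The treatment coefficient's meaning depends on the coding, but recoding time leaves the fit unchanged, and visit-specific or averaged differences derived from it do not depend on the origin.
- *A second thresholded contrast is required.* It would be a trade-off, with the costs shown above.

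The missing sign has a partial answer, since section 18.1 is directional. But the gloss in section 18.8.2 is not, and the 40% figure applies only if direction really is ignored.

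**Conclusion.** The point holds as a limitation of the focal quantity. The interaction cannot tell a benefit maintained from month 6 from no effect (20% favourable and 20% unfavourable in both cases). It points the wrong way for a 0.2 SD benefit that fades (about 56% unfavourable). It therefore covers only part of the hypothesis in section 18.1.

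The result for a maintained benefit follows from the contrast and does not depend on the correlations. The 56% and 88% figures do depend on them, and on equal arms, unit SD, a flat prior and no covariate adjustment; they are illustrative. A reader might infer that the 92% is wrong. That does not follow: the scale of the assumed effect and the exact posterior statement are not given, so the figure cannot be verified either way.

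**What to change.** Keep the interaction as the sized term and state in section 18.8.2 which sign is favourable.

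In sections 18.8.1 and 18.8.2, prespecify that two treatment differences in pulmonary capacity, at month 6 and averaged over months 6, 12 and 24, will be derived from the fitted model. Report both beside the interaction with posterior probability of benefit and credible interval, and say that the interaction will be interpreted together with them. This needs no second success threshold and does not depend on how time is coded. A fit with visit as a categorical factor can be a stated sensitivity model. It is a different mean model from the linear slope and should be labelled as such.

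Give the averaged contrast's precision as illustrative (SE about 0.10 SD; about 88% for a maintained 0.2 SD, or 73–84% at constant correlation 0.8–0.3), re-run under the priors of section 18.8.3. If the sponsor does choose a threshold for both contrasts, report the joint false-positive rate and the interaction's loss of detection at 0.90.

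The cost is wording and a re-run of the simulation; no visits or data are added. The downside is that the level contrast compares consenting survivors and is open to selection, so deaths and follow-up consent should be reported by arm beside it. The change carries most weight if made before outcome data by arm are seen.

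### The 92% power for the long-term follow-up cannot be reproduced from the inputs in section 18.8.2, and the null detection rate of the 0.80 rule is not reported

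*Combined protocol and SAP*

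**What the plan says.** Section 18.8.2 assumes a small standardised effect (d = 0.2) "unfolding in linear fashion over time (6, 12, and 24 months"). The within-subject correlation is 0.3 at a six-month lag, "with this correlation diminishing by 50% for every additional six-month time lag". On sample size, 200 are to be enrolled, and the authors "assume attrition will be approximately 10% resulting in a final sample of n = 180". The decision rule is a posterior probability of 0.80 for an interaction, glossed as "there is an 80% chance that there are differential trajectories of change for the treatments". The reported result is that "K = 1000 Monte Carlo simulations identify an interaction term 92% of the time".

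Section 18.8.3 describes the analysis: "Generalized linear multilevel models will evaluate change as a function of time, treatment, and the interaction of treatment and time". On priors it says "Prior distributions will be neutral (centered on the null hypothesis) and weakly informative", without a scale, and it plans checks under alternative priors. Section 13.2 does give a scale (variance 10) in a sentence that begins "For all generalized linear models, priors for regression coefficients will be specified as ~Normal", but nothing says whether it carries over to section 18.

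Section 12, for the day-14 outcome, reports a Type I error beside each power figure (3.5%, 4.8% and 3.7%). Section 18.8.2 has no counterpart.

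**The concern.** The power depends on how much the gap between arms widens from month 6 to month 24. Section 18.8.2 does not say over what span the 0.2 applies, how time is coded, whether the 0.80 rule counts one direction or either, or which prior was simulated. A 0.2 SD effect with about 90 per arm is hard to detect as a slope difference, even under a lenient rule, so 92% looks high.

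Two things are at stake. This paragraph is the only sample-size justification for the follow-up, whose primary objective in section 18.2 includes this interaction. And a detection rate under the alternative cannot be weighed without the rate of the same rule under no effect.

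**Working it through.** **Inputs from the plan.** Visits at 6, 12 and 24 months. Correlations of 0.30 (months 6 and 12, lag 6), 0.15 (months 12 and 24, lag 12) and 0.075 (months 6 and 24, lag 18). 180 analysed and a 0.80 posterior rule (18.8.2). 1:1 allocation (section 4).

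**Assumptions.** 90 per arm, unit SD and complete data at each visit, one linear slope difference, no precision gain from the stratification covariates, and a near-flat prior unless stated.

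**Standard error.** The arm differences at the three visits have covariance 2V/90, where V is the correlation matrix above. Generalised least squares with an intercept and a slope in months gives SE(slope difference) = 0.01119 SD per month. Over the 18 months from month 6 to month 24 this is 18 × 0.01119 = 0.2015 SD.

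**Power formula.** With z = widening / 0.2015 and 0.842 as the 80th normal percentile, one-direction power is Φ(z − 0.842). Counting either direction adds Φ(−z − 0.842).

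**Attempt to reproduce 92%.**

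| Reading of d = 0.2 | Gap at months 6 / 12 / 24 | z | One direction | Either |
|---|---|---|---|---|
| 0.2 at month 24, from 0 at randomisation | 0.05 / 0.10 / 0.20 | 0.15/0.2015 = 0.744 | 46.1% | 51.8% |
| 0.2 at month 24, from 0 at month 6 | 0 / 0.067 / 0.20 | 0.20/0.2015 = 0.993 | 56.0% | 59.3% |
| 0.2 per 12 months | 0.10 / 0.20 / 0.40 | 0.30/0.2015 = 1.489 | 74.1% | 75.1% |
| 0.2 per visit, equal steps | 0 / 0.20 / 0.40 | 1.937 (fitted slope) | 86.3% | 86.6% |
| 0.2 per visit on average, linear in months | 0 / 0.133 / 0.40 | 0.40/0.2015 = 1.985 | 87.4% | 87.6% |
| 0.2 per six months | 0.20 / 0.40 / 0.80 | 0.60/0.2015 = 2.978 | 98.4% | 98.4% |

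None gives 92%. Simulation error does not close the gap: 1.96 × √(0.92 × 0.08/1000) = 0.017, so K = 1000 runs allow about 90.3% to 93.7%. A simpler random-intercept fit to the same data moves the powers by about 3 points or less.

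**What 92% would need.** The 92nd normal percentile is 1.405, so the widening must be (0.842 + 1.405) × 0.2015 = 0.453 SD. Keeping the widening at 0.2 SD instead needs about 90 × (0.453/0.2)² ≈ 460 analysed per arm.

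**Routes that land near 92%.** Taking 0.2 per visit with a constant correlation of 0.3 gives 91.7% to 92.9% in one direction, but contradicts the stated halving. Taking 0.2 per population SD of visit time (SD of 6, 12, 24 = 7.48 months, so a widening of 0.2 × 18/7.48 = 0.481 SD) gives 93.9%. That keeps every stated input but uses a scaling the text does not mention.

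**Detection rate under no effect.** With z = 0 and a near-flat prior, the rate is Φ(−0.842) = 20% in one direction and 2 × 20% = 40% in either. With a neutral normal prior of SD τ on the month 6 to 24 change, the cut-off on z becomes 0.842/√w, where w = τ²/(τ² + 0.2015²):

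| τ | One direction | Either | One-direction power, 0.2 SD widening |
|---|---|---|---|
| near-flat | 20.0% | 40.0% | 56.0% |
| 1 | 19.5% | 39.1% | 55.3% |
| 0.5 | 18.2% | 36.4% | 53.4% |
| 0.2 | 11.6% | 23.2% | 42.0% |

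The section 13.2 prior (variance 10), if it applies, leaves the null rates at 19.95% to 20.0% and 39.9% to 40.0%.

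**The case against.** The strongest defence is that the paragraph is underspecified rather than miscalculated. A reader might infer from the table that 92% is wrong. The documents do not support that: 92% lies inside the 46% to 98% span of readings, and 0.2 per population SD of visit time keeps one slope, the stated correlations and n = 180. With a neutral prior of assumed SD 0.2 on that standardised coefficient, this reading gives 93.0%, within simulation error of 92%. That stands. The scaling is still unstated, however, and it is sensitive: using the sample SD of visit time gives 86.6% under a flat prior.

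A reader might also take 20% or 40% as the trial's false-positive rate. That too goes beyond the text. Section 18.8.3 intends regularising priors and checks under more sceptical ones, so under a correctly specified model with a neutral prior these figures are upper bounds. They are close to the truth only if the prior is wide, and the plan does not say how wide it is.

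Finally, 0.80 is stipulated for sizing. Section 18.8 sets no declaration of superiority like the one in section 12, and section 2.7 argues for posterior probabilities over error-rate control in early testing. So there is no ground for saying that the follow-up will declare an effect at this error rate, or that the cut-off must match section 12, whose rule and endpoint differ. But the sponsor reports Type I error for its own Bayesian rule in section 12, so the same disclosure here follows its own practice.

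**Conclusion.** The point holds as a failure to reproduce together with an omission. On the plain reading, with d = 0.2 as the gap reached by month 24, power is about 46% to 59% against the stated 92%. Wider readings give 74% to 75%, 86% to 88% and 98%. A widening of about 0.45 SD is more than twice the effect the section calls small. The null detection rate is unreported; it is about 20% in one direction or 40% in either under a near-flat prior, and lower under a tighter one.

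These figures rest on the assumptions listed with the calculation: equal arms, equal SDs, complete data on 180 and a single linear slope. Which reading the sponsor simulated is not known. The effect is confined to the optional long-term follow-up; the day-14 primary outcome and N = 650 are untouched. It should be fixed.

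**What to change.** In section 18.8.2:

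1. State the assumed between-group gap, in SD units, at months 6, 12 and 24.
2. State how time is coded and that the interaction is a single slope difference, or otherwise which terms count.
3. State whether the 0.80 rule counts one direction or either.
4. State the prior used in the simulation with its scale, and whether the section 13.2 coefficient prior applies to section 18.
5. Re-run the simulation on those inputs, replace 92% with the result, and report the Type I error beside it, as section 12 does.

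The cost is one re-run of an existing simulation and a revised paragraph, with no added participants or visits. The downside is that the stated power will probably be less favourable, and the null detection rate, once visible, may prompt discussion of a stricter cut-off, which would lower power further.
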